## **7.2 Study completion and post-study treatment**

Each patient will be required to complete the study in its entirety and thereafter no further study treatment will be made available to them. Study completion is defined as when the last patient completes their End of Study visit, and any repeat assessments associated with this visit have been documented and followed-up appropriately by the Investigator, or in the event of an early study termination decision, the date of that decision.

### **7.2.1 Lost to follow-up**

For patients whose status is unclear because they fail to appear for study visits without stating an intention to discontinue or withdraw, the investigator should show "due diligence" by documenting in the source documents steps taken to contact the subject, e.g. dates of telephone calls, registered letters, etc. A subject should not be formally considered lost to follow-up until his/her scheduled end of study visit would have occurred.

## **7.3 Withdrawal of consent**

Subjects may voluntarily withdraw consent to participate in the study for any reason at any time. Withdrawal of consent occurs only when a subject:

- Does not want to participate in the study anymore, and
- Does not allow further collection of personal data

In this situation, the investigator should make a reasonable effort (e.g. telephone, e-mail, letter) to understand the primary reason for the subject's decision to withdraw his/her consent and record this information.

Study treatment must be discontinued and no further assessments conducted, and the data that would have been collected at subsequent visits will be considered missing.

Further attempts to contact the subject are not allowed unless safety findings require communicating or follow-up.

All efforts should be made to complete the assessments prior to study withdrawal. A final evaluation at the time of the subject's study withdrawal should be made as detailed in the assessment table.

Novartis will continue to keep and use collected study information (including any data resulting from the analysis of a subject's samples until their time of withdrawal) according to applicable law.

For US sites: All biological samples not yet analyzed at the time of withdrawal may still be used for further testing/analysis in accordance with the terms of this protocol and of the informed consent form.

For EU and RoW sites: All biological samples not yet analyzed at the time of withdrawal will no longer be used, unless permitted by applicable law. They will be stored according to applicable legal requirements.

#### **7.4 Study Stopping rules**

The study will be paused and no further dosing will be conducted pending a full, unblinded safety review if any of the following criteria are met:

- One or more SAE's are reported
- If 2 or more patients experience an AE that is similar and of severe grade
- If 2 or more patients have their infusion discontinued for safety or tolerability reasons
- A CLR325-treated patient develops anti-apelin antibodies
- The principal investigator and the sponsor consider that the number and/or severity of adverse events justify discontinuation of the study
- The sponsor unilaterally requests it

#### **7.5 Early study termination**

The study can be terminated at any time for any reason by Novartis. Should this be necessary, patients should be seen as soon as possible and treated as a prematurely withdrawn patient. The investigator may be informed of additional procedures to be followed in order to ensure that adequate consideration is given to the protection of the patient's interests.

The investigator will be responsible for informing IRBs/IECs of the early termination of the trial.

## 8 Procedures and assessments

**Table 8-1 Assessment Schedule**

Study Phase	Screening	Baseline	Treatment												Follow-up	EOS
Visit Numbers 	V1	V2	V3												V4	V777
Study Day(s) (windows)	-45 to 1	1	1 to 2												10 (-3 +3)	28 (-5 +5)
Time (post-dose)	-	-	-1h 	0h	1h	3h	6h	8h	10h	12h	18h	20h	24h	28h	-	-
Informed consent	X															
CCI		X														
Inclusion / Exclusion criteria	X	X														
Medical history/current medical conditions	X	X														
Concomitant therapies	X	X														
Demography	X															
Alcohol Test and Drug Screen	X															
Hepatitis 	X															
Pregnancy test	X	X 														
Body weight	X	X											X		X	X
Fluid Input and Output			X													
Vital Signs	X	X	X 												X	X
Physical examination	X	X											X 		X	X
Hematology	X	X					X			X	X		X		X	X
Blood chemistry	X	X					X			X	X		X		X	X
Coagulation	X	X								X			X		X	X
Urinalysis	X	X											X		X	X
28-hr urine collection			X 													

Study Phase	Screening	Baseline	Treatment												Follow-up	EOS	
Visit Numbers 	V1	V2	V3												V4	V777	
Study Day(s) (windows)	-45 to 1	1	1 to 2												10 (-3 +3)	28 (-5 +5)	
Time (post-dose)	-	-	-1h 	0h	1h	3h	6h	8h	10h	12h	18h	20h	24h	28h	-	-	
ECG evaluation	X	X		X 			X 			X 	X 		X 	X 	X	X	
CCI		X															
PK blood collection 	See table below																
CCI	See table below																
	See table below																
	See table below																
	See table below																
Immunogenicity		X													X	X	
Cardiac Hemodynamic monitoring 		X	X														
PA catheter derived Cardiac Output 			X														
Mixed venous blood gas 			X														
Telemetry cardiac monitoring 			X														
Echocardiogram 		X	X														
AICD Interrogation 		X														X	
Study drug administration				X													
Subjects domiciled			X														
Study completion information																X	
AEs and SAEs	X 																

 Visit structure given for internal programming purpose only

 (-) 1 hour assessments need to be at LEAST 1 hour prior to dose administration.

Study Phase	Screening	Baseline	Treatment												Follow-up	EOS
Visit Numbers 	V1	V2	V3												V4	V777
Study Day(s) (windows)	-45 to 1	1	1 to 2												10 (-3 +3)	28 (-5 +5)
Time (post-dose)	-	-	-1h 	0h	1h	3h	6h	8h	10h	12h	18h	20h	24h	28h	-	-

 If obtained within the past 2 months, sites may confirm with proper documentation that Hepatitis serologie's have been evaluated.

 Urine dipstick

 Vital signs will be measured manually by staff. At hour 0 a complete set of vital signs will be measured. Blood pressure and pulse rate will be measured during treatment period timepoint: 15 minutes, 30 minutes and 45 minutes post dose. A complete set of vital signs will be measured hourly thereafter, from hour 1 to hour 28. Complete vital signs consist of Blood Pressure, Pulse Rate, Body Temperature, Respiratory Rate and Oxygen Saturation. For the hourly vital sign assessments there is a window of +/- 10 minutes.

For the physical exam performed during treatment period (at 24h), a +/- 30 min window is allowed.

 Patient should void prior to the start of the infusion. Urine collection for 28 hours will begin at the start of infusion.

 ECG may be evaluated up to 45 minutes prior to t=0.

 Assessment windows for ECGs during Treatment may be +/- 30 minutes.

 Assessment window for PK blood collection during Treatment period at 0 hour may be within 60 min prior to start of infusion. A +/- 5 min window is allowed post start of infusion up to 28 hours post infusion. See Table 6-1 of SOM.

 Continuous Cardiac Hemodynamics will be monitored using a pulmonary artery catheter, every 15 minutes from hour -1 to hour 1 in the treatment period, and hourly for the remainder of the treatment period. See SOM for more details.

### Corporate Confidential Information

 3 lead continuous telemetry to begin pre-dose and will be discontinued up to 28 hours post infusion.

 For echocardiography cohorts only. Sites will be notified if echo will be performed (for the full cohort).

 If patient has AICD in place.

 As required

**Details for highly repetitive assessments**

Study Phase	Visit	Day	Time (post-dose)	PK blood collection		Corporate Confidential Information		
Screening	V1	-45 to 1	-				X	
Baseline	V2	1	-					
Treatment	V3	1 to 2	-1h 					
			0h	X	X	X	X	X
			0.5h	X				
			1h					
			3h	X				
			5h	X				
			6h					
			8h	X				
			10h	X				
			12h	X				
			18h	X	X	X	X	X
			20h	X				
			24h	X				
			28h	X	X	X	X	X
Follow-up	V4	10 -3 +3	-	X	X	X	X	X
EOS	V777	28 -5 +5	-	X	X	X	X	X

 (-) 1 hour assessments need to be at LEAST 1 hour prior to dose administration.

## **8.1 Informed consent procedures**

Eligible patients may only be included in the study after providing written (witnessed, where required by law or regulation), IRB/IEC-approved informed consent.

If incapable of doing so, in cases where the patient's representative gives consent, the patient should be informed about the study to the extent possible given his/her understanding. If the patient is capable of doing so, he/she should indicate assent by personally signing and dating the written informed consent document or a separate assent form.

Informed consent must be obtained before conducting any study-specific procedures (i.e. all of the procedures described in the protocol). The process of obtaining informed consent should be documented in the patient source documents.

The date of signing of informed consent (and withdrawal, if later withdrawn) should be documented in the CRF.

Novartis will provide to investigators a proposed informed consent form that complies with the ICH GCP guideline and regulatory requirements and is considered appropriate for this study. Any changes to the proposed consent form suggested by the investigator must be agreed to by Novartis before submission to the IRB/IEC.

Pregnancy outcomes must be collected for the female partners of any males who took study treatment in this study. Consent to report information regarding these pregnancy outcomes should be obtained from the mother.

## **Corporate Confidential Information**

## **8.2 Subject demographics/other baseline characteristics**

Demographic and baseline characteristic data will be collected on all patients.

Relevant medical history/current medical conditions data includes data until signature of informed consent. Where possible, diagnoses and not symptoms will be recorded.

Investigators have the discretion to record abnormal test findings on the medical history CRF whenever in their judgment, the test abnormality occurred prior to the informed consent signature.

## Corporate Confidential Information

### 8.3.2 Invasive hemodynamic monitoring

For PA catheter cohorts, the clinically indicated pulmonary artery catheter placed prior to entry into the study will remain in place until the end of the treatment period. The following parameters are measured:

- Right atrial pressure (RAP) in mmHg
- Systolic and diastolic right ventricular pressure (RVP) in mmHg – only required in patients with a PA catheter with RV ports capable of measuring RV pressures.
- Systolic and diastolic pulmonary arterial pressure (PAP) in mmHg
- Pulmonary capillary wedge pressure (PCWP) in mmHg
- Cardiac output (CO) in L/min
- Brachial systolic blood pressure (SBP), diastolic blood pressure (DBP), and heart rate - measured with each set of hemodynamic measurements

In addition pulse oximetry will be used to measure

- Peripheral arterial oxygen saturation SaO2 in %

Derived hemodynamic parameters are:

- Systemic vascular resistance (SVR) in dynes•sec/cm^5
- Pulmonary vascular resistance (PVR) in dynes•sec/cm^5
- Mean PAP in mmHg
- Stroke volume (SV) in mL
- Cardiac index (CI) in L/min/m^2

The hemodynamic measurements are repeated as indicated in the Site Operations Manual. In the event of any clinically significant change in hemodynamic measurements, additional hemodynamic measurements will be obtained at greater frequency as outlined in the Site Operations Manual. The hemodynamic measurements are done immediately before blood

collection at each time point. All hemodynamic parameters will be entered in the eCRF. Details of the hemodynamic measurements will be described in the Site Operations Manual.

### **8.3.3 Echocardiogram**

A limited echocardiogram will be performed for an entire dosing cohort for those cohorts designated by the sponsor as echocardiography cohorts. If the site enrolls a subject in the echocardiographic cohort, the baseline scan will be evaluated locally to confirm patients with a lateral E/E' ratio of  $<7$  will be excluded.

The complete technical details of the equipment and machine settings will be captured in a separate echocardiographic manual prepared by an imaging CRO who will perform all analysis for determining cardiac output, ventricular volumes, and left ventricular ejection fraction. In brief, a Doppler flow evaluation to determine the blood flow velocity across the aortic valve will be acquired over multiple cardiac cycles which, along with heart rate, will be used to determine cardiac output. Additional measurements of ventricular volumes (systole and diastole) and left ventricular ejection fraction will also be captured. The image data will be collected from sites by an imaging CRO for central reading and reporting of the quantitative image analysis. A detailed Echocardiogram Manual will be provided to all sites participating in this imaging assessment which includes the acquisition and image transfer details.

### **8.3.4 Mixed venous blood gas (SvO2)**

For PA catheter cohorts, a blood sample will be withdrawn from the PA catheter for a measurement of oxygen saturation (SvO2) at the times indicated in the [Assessment Schedule](#).

## **8.4 Safety**

Safety assessments are specified below; methods for assessment and recording are specified in the Site Operations Manual, with the [Assessment Schedule](#) detailing when each assessment is to be performed.

### **8.4.1 Physical examination**

A complete physical examination will include the examination of general appearance, skin, neck (including thyroid), eyes, ears, nose, throat, lungs, heart, abdomen, back, lymph nodes, extremities, vascular and neurological. If indicated based on medical history and/or symptoms, rectal, external genitalia, breast, and/or pelvic exams may be performed.

Information for all physical examinations should be included in the source documents and will not be transferred to the sponsor as part of the study analysis. Significant findings that are present prior to informed consent are included in the Relevant Medical History section of the source documents. Significant findings observed after informed consent signature which meet the definition of an Adverse Event must be appropriately recorded on the Adverse Event eCRF section.

### 8.4.2 Vital signs

Vital signs include blood pressure (BP), pulse rate, respiratory rate, body temperature and peripheral oxygen saturation (SaO2). After the subject has been supine for approximately 5 minutes systolic and diastolic BP will be measured once using an automated validated device, with an appropriately sized cuff. In case the cuff sizes available are not large enough for the subject's arm circumference, a sphygmomanometer with an appropriately sized cuff may be used.

### 8.4.3 Height and weight

Height in centimeters (cm) (without shoes) will be measured.

Body weight (to the nearest 0.1 kilogram [kg] in indoor clothing, but without shoes) will be measured.

Body mass index (BMI) will be calculated using the following formula:

- $BMI = \text{Body weight (kg)} / [\text{Height (m)}]^2$

### 8.4.4 Laboratory evaluations

Clinically relevant deviations of laboratory test results occurring during or at completion of the study must be reported and discussed with Novartis personnel. The results should be evaluated for criteria defining an adverse event and reported as such if the criteria are met. Repeated evaluations are mandatory until normalization of the result(s) or until the change is no longer clinically relevant. In case of doubt, Novartis personnel should again be contacted.

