## 2 Study objectives

### 2.1 Primary objective(s)

Primary objective(s)	Endpoints related to primary objective(s)

To determine the safety and tolerability of an 18-hour i.v. infusion of CLR325 in stable heart failure patients.

	

Frequency of adverse events in CLR325 treated patients as compared to patients treated with placebo.

Frequency of clinically significant changes in hematology or clinical chemistry laboratories or changes in blood pressure or heart rate.

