## **6.5 Treatment blinding**

The sponsor will be unblinded to treatment during this study. Patients, investigator staff, and persons performing the assessments will remain blind to the identity of the treatment from the time of randomization until database lock, using the following methods:

1. Randomization data are kept strictly confidential until the time of unblinding, and will not be accessible by patients, site staff, and study investigators with the exception of the unblinded site pharmacy staff.
2. The identity of the treatments will be concealed by the use of study drugs that are all identical in packaging, labeling, and schedule of administration.

See the Site Operation Manual for further details on blinding.

Unblinding will only occur in the case of subject emergencies ([Section 6.6](#)) and at the time of the interim analysis (see [Section 3.5](#)) and at the conclusion of the study. An assessment will be done by the appropriate site personnel and the sponsor for any subject whose treatment code has been broken inadvertently or for any non-emergency reason to assess whether or not study drug should be discontinued.

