### 8.4.5 Electrocardiogram (ECG)

ECG evaluations will be obtained at specific time points specified in the [Assessment Schedules](#).

A standard 12-lead ECG will be performed with the subject in a supine position. Interpretation of the tracing must be made by a qualified physician and documented on the ECG and in the ECG section of the source document. Each ECG tracing should be labeled with the

- study number
- patient initials
- patient number
- date

and kept in the source documents at the study site. Clinically significant abnormalities should be recorded on the relevant medical history eCRF page prior to informed consent signature and on the Adverse Events page thereafter. Clinically significant findings must be discussed with the sponsor.

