**Corporate Confidential Information**

## Corporate Confidential Information

### 9 Safety monitoring

#### 9.1 Adverse events

An adverse event (AE) is any untoward medical occurrence (i.e., any unfavorable and unintended sign [including abnormal laboratory findings], symptom or disease) in a subject or clinical investigation subject after providing written informed consent for participation in the study. Therefore, an AE may or may not be temporally or causally associated with the use of a medicinal (investigational) product.

The occurrence of adverse events should be sought by non-directive questioning of the patient at each visit during the study. Adverse events also may be detected when they are volunteered by the patient during or between visits or through physical examination, laboratory test, or other assessments.

Abnormal laboratory values or test results constitute adverse events only if they fulfill at least one of the following criteria:

- they induce clinical signs or symptoms,
- they are considered clinically significant,
- they require therapy.

Clinically significant abnormal laboratory values or test results should be identified through a review of values outside of normal ranges/clinically notable ranges, significant changes from baseline or the previous visit, or values which are considered to be non-typical in patients with underlying disease. Investigators have the responsibility for managing the safety of individual subject and identifying adverse events. Alert ranges for liver related events are included in [Section 9.3](#).

Adverse events must be recorded on the Adverse Events eCRF for patients that pass screening and enter into the study. The adverse events should be reported according to the signs, symptoms or diagnosis associated with them, and accompanied by the following information:

1. The severity grade AE grade
  - mild: usually transient in nature and generally not interfering with normal activities
  - moderate: sufficiently discomforting to interfere with normal activities
  - severe: prevents normal activities
2. Its relationship to the study treatment

3. Its duration (start and end dates) or if the event is ongoing an outcome of not recovered/not resolved should be reported.
4. Whether it constitutes a serious adverse event (SAE). See [Section 9.2](#) for definition of SAE

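### Laboratory deviations must be discussed with an unblinded sponsor, and the protocol does not require the blinded investigator's significance and adverse-event decision to be recorded first

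*Protocol*

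**What the plan says.** **Who knows the treatment.** Protocol Section 6.5 opens with "The sponsor will be unblinded to treatment during this study". It then lists who does not know: "Patients, investigator staff, and persons performing the assessments will remain blind to the identity of the treatment from the time of randomization until database lock". The sponsor statement carries no exception, and the reader is sent to the Site Operations Manual for more detail on blinding.

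**Laboratory findings.** Section 8.4.4 says: "Clinically relevant deviations of laboratory test results occurring during or at completion of the study must be reported and discussed with Novartis personnel". The next sentence is "The results should be evaluated for criteria defining an adverse event and reported as such if the criteria are met". Testing is then repeated until the value normalises or stops being clinically relevant, and the paragraph ends: "In case of doubt, Novartis personnel should again be contacted".

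**ECG findings.** Section 8.4.5 has a qualified physician interpret and document the tracing. It says where clinically significant abnormalities are to be recorded (medical history before consent, the Adverse Events page after it). Then it adds: "Clinically significant findings must be discussed with the sponsor".

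**What makes a test result an adverse event.** Section 9.1 gives three alternative criteria. One is that "they are considered clinically significant". The same section makes investigators responsible for identifying adverse events.

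**What is compared.** The first primary endpoint in Section 2.1 is "Frequency of adverse events in CLR325 treated patients as compared to patients treated with placebo". The second covers clinically significant hematology or chemistry changes, together with blood pressure and heart rate. Section 11.4.2 compares adverse-event occurrence between arms with Fisher's exact test.

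**The concern.** A blinded investigator protects a harm comparison only as far as the decisions that create events are made without knowledge of the arm. Here one such decision, whether a laboratory change is clinically significant, is a matter of judgement and is enough by itself to create an event. The protocol attaches to it a compulsory conversation with an organisation that it describes as unblinded. No code has to be disclosed for this to matter: advice that a change is or is not of concern can differ by arm without anyone intending it.

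At stake is whether the CLR325 and placebo percentages for laboratory-based events are ascertained in the same way. These are primary endpoints, and the numbers are small, so a few decisions can move them visibly.

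**Working it through.** **1. Does the text separate the decision from the unblinded party?**

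| Step | Laboratory (8.4.4) | ECG (8.4.5) |
|---|---|---|
| What triggers the discussion | A deviation the site already regards as clinically relevant | A finding already called clinically significant |
| Discussion with sponsor | Compulsory | Compulsory |
| Place of the adverse-event evaluation in the text | Sentence after the discussion | Recording mentioned before the discussion |
| Order fixed by the wording | No | No |
| Further contact when unsure | Yes | Not stated |
| Route to the primary endpoints | Adverse events, and laboratory changes directly | Adverse events only |

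For laboratory results, sentence order suggests discussion first but does not impose it. For ECGs, sentence order points the other way. In neither section does the text say that the investigator's decision is recorded first, or that the sponsor contact lacks the codes. Section 10.3, by contrast, specifies a blinded expert reader for echocardiograms.

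**2. The protocol's own figures.** The protocol gives no figure for this issue. Its only related numbers are in Section 11.6: the chance of at least one active subject with a given event at a 20% rate.

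- 6 active: 1 − 0.80^6 = 73.8% (stated 74%).
- 4 active: 1 − 0.80^4 = 59.0% (stated 60%).

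Both reproduce to within about a point. They assume that every event is recorded. If only 80% or 50% of true events on CLR325 were recorded (assumed values), the recorded rate would be 0.20 × 0.80 = 16% or 0.20 × 0.50 = 10%. The chance of seeing at least one among 6 would then be 1 − 0.84^6 = 64.9% or 1 − 0.90^6 = 46.9%.

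**3. Size of a between-arm gap, by assumption only.** Suppose 30% of patients in both arms truly have a qualifying finding, and a share of one arm's findings is set aside as not significant.

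- Share 10%: 0.30 × 0.90 = 27.0%, a gap of 3 points.
- Share 25%: 0.30 × 0.75 = 22.5%, a gap of 7.5 points.

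Neither the 30% nor the 10% to 25% comes from the documents, and either arm could be the one affected.

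**4. What one decision is worth.** The first cohort is 6 CLR325 and 2 placebo. One patient reclassified moves the placebo percentage by 1/2 = 50 points or the active percentage by 1/6 = 16.7 points. If the 6:2 ratio were kept up to the maximum of 40 (an assumption), the arms would be 30 and 10. One patient would then be 3.3 or 10 points. On that basis, the 3 to 7.5 point gap corresponds to 0.9 to 2.25 patients on CLR325, or 0.3 to 0.75 of a patient on placebo.

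**The case against.** The case against is substantial, and several parts of it stand.

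- **The blinded investigator decides.** Section 9.1 gives the investigator responsibility for identifying adverse events, and nothing gives the sponsor a vote or veto. This is correct, and it limits the concern to influence. It does not remove the concern, because the consultation is compulsory and may come before the decision.
- **The order is not stated.** A reader might infer that the sponsor is always consulted before the adverse-event decision. The text does not support that. For laboratory results the order is only implied, the site must already think the deviation relevant, and the second contact may concern when follow-up can stop. For ECGs, interpretation and recording are mentioned first.
- **Much of the endpoint is untouched.** A reader might infer that the primary endpoints as a whole rest on these discussions. They do not. Adverse events also come from questioning, volunteered reports and examination. Blood pressure and heart rate are outside Sections 8.4.4 and 8.4.5, and the second endpoint does not name ECG. Sections 11.4.2 and 11.5.2 also list and summarise all laboratory values by arm, flagging abnormalities where ranges exist. This gives a partial check that does not depend on the judgement.
- **Re-testing.** A reader might infer that extra repeat tests in one arm would inflate its event rate. Under Section 8.4.4, repeats follow a deviation already found and are compulsory in both arms. Section 11.4.2 reports subjects and counts each once per body system. Repeating the test in a patient who already has the event adds nothing to that percentage.
- **The manual may settle it.** A reader might infer that the person taking the site's call definitely knows the arm. The Site Operations Manual is not at hand, and parts of the protocol are redacted, so who holds the codes cannot be established. However, any separation described there would conflict with the unqualified opening of Section 6.5. That section also says unblinding occurs only in emergencies, at the interim analysis and at study end, which fits poorly with a sponsor unblinded throughout.
- **An unblinded sponsor and a non-confirmatory aim are normal at this stage.** Agreed. The point is only about who advises on individual findings, and when.

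**Conclusion.** The point holds in a limited form. The protocol requires laboratory deviations that the site thinks clinically relevant to be discussed with an unblinded sponsor. It lets a judgement of clinical significance alone turn a result into a primary-endpoint event, and it does not say that the blinded investigator's decision is made and recorded first. That leaves an avoidable route to differential ascertainment. The ECG route is secondary.

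The documents establish neither the existence of a bias nor its size or direction. The 3 to 7.5 point gap rests entirely on the assumed 30% rate and the assumed 10% to 25% reclassification. In the largest trial considered here it amounts to less than one placebo patient, or about one to two CLR325 patients. The reason to act is that the route is plain on the page and closing it costs almost nothing.

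**What to change.** **Main change, Section 8.4.4 (and Section 8.4.5 for clarity).** State that the blinded investigator records the clinical-significance and adverse-event decision, with severity and relationship to study treatment, in the eCRF before the finding is discussed with the sponsor. State also that this must not delay any urgent safety contact, and that a later change to the decision stays in the audit trail with a reason. The two states of the record can then be compared by arm.

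**Secondary change, where sponsor staffing allows.** Route discussions of single laboratory and ECG findings through sponsor personnel without access to treatment codes, and reword the first sentence of Section 6.5 to match. Other sponsor staff can remain unblinded for cohort and safety decisions. If the Site Operations Manual already separates these roles, it is enough to say so in Section 6.5.

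**Cost.** Protocol wording, a short site instruction and possibly an access restriction. No extra patients, visits, samples or procedures are needed, and no sample-size figure changes. The small downside of the secondary change is that the site's contact cannot use treatment knowledge when advising on one finding. Unblinded sponsor colleagues and the emergency code break in Section 6.6 remain available.
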